Aim 1: Test the effect of dynamic social norms, messenger effects, and processing fluency messages on hypertension medication adherence. The study team will identify 59,997 Medicare Advantage beneficiaries insured by Humana who are not fully adherent to hypertension medications and randomize them to one of six mailed communications to increase medication adherence or control. The primary outcome will be medication adherence (measured by pharmacy refill claims).

Aim 2: Assess association of claims and demographic characteristics with intervention responsiveness. The study team will evaluate the impact of the interventions as a function of baseline levels of adherence, demographic characteristics, and clinical comorbidities to determine the association of patient characteristics with intervention responsiveness. These profiles could be used to target future message content and framing to specific patients most likely to respond.

[figure not shown]
Design and Outcomes

Design: randomized controlled clinical trial of patient-facing messages to test the impact of social norms, messengers, and processing fluency on hypertension medication adherence in individuals 65 to 79 years of age taking medication for hypertension with adherence levels (based on the proportion of days covered metric [PDC]) between 60% and 85%.

The primary outcome will be the average end-of-year PDC in each arm. A secondary outcome will be the proportion of study participants with end-of-year PDC \geq 80%.

See **Figure 1** for an overview of the study design.

Figure 1: Overview of Study Design

Interventions and Duration

Study participants will be randomly assigned to one of seven conditions:

1. A scorecard from Humana reporting patients' medication adherence using a "refill score"
2. The Arm 1 scorecard plus dynamic social norms messaging (noting the proportion of Humana members improving their medication refill scores)
3. The Arm 1 scorecard, coming from the trusted messenger of a Humana-identified pharmacist taking the same medication

4. A modified scorecard increasing processing fluency through a visual metaphor of “closing the ring”
5. The Arm 4 scorecard plus dynamic social norms messaging
6. The Arm 4 scorecard, coming from the trusted messenger of a Humana-identified pharmacist taking the same medication
7. No mailed message (usual care)

Participants will participate in this study for approximately 6 months (through December 2023).

Sample Size and Population

Target population: 59,997 Humana Medicare patients 65 to 79 years of age taking hypertension medications with adherence level (based on the proportion of days covered metric [PDC]) between 60% and 85%. Divided across 7 arms, there will be 8,571 participants in each arm. Randomization will be stratified by whether participants are on a 30-day medication refill cycle (~26% of overall study population) or a 90-day medication refill cycle (~74% of overall study population).

STUDY TEAM ROSTER

Principal Investigator: **[name], MBA, BCACP**
Humana, Inc.
[name]
[name]
[contact]
[contact]

Main responsibilities/Key roles: Responsible for overseeing the trial execution and evaluation activities; oversight of activities related to the trial execution and evaluation of the effectiveness of the interventions; overseeing the activities of the sub-investigators and study staff.

PARTICIPATING STUDY SITES

Study participants will be selected from Humana, a large insurance provider.

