4 SELECTION AND ENROLLMENT OF PARTICIPANTS

4.1 Inclusion Criteria

Patients must meet all inclusion criteria to participate in this study:

- Medicare Advantage beneficiary insured by Humana
- Between the ages of 65 and 79
- Having at least two unique fills of any class of hypertension medication within the calendar year
- Adherence level (as measured by the proportion of days covered [PDC] metric) between 60% and 85%

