6 STUDY PROCEDURES

6.1 Schedule of Evaluations

Assessment	Baseline, Enrollment, Randomization: (Day 0)	Treatment 1 (Day 1)	Treatment 2 (Day 53)	Final analysis
Identification of eligible patients	X			
Enrollment/Randomization	X			
Intervention (control and experimental)		X	X	
Outcome analysis				X

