6.2 Description of Evaluations

6.2.1 Screening Evaluation

Consenting Procedure

As with other minimal-risk, quality improvement studies the study team has performed that involve the use of routine clinical tools such as patient portals and reminder letters, formal informed consent will not be sought.

Screening

Eligibility decisions will be decided based on age and adherence level in July 2023.

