9.2.1 Treatment Assignment Procedures

Study participants will be randomized in a 1:1:1:1:1:1:1 ratio with a random number generator into one of 7 arms, stratified by whether participants are on a 30-day

medication refill cycle (~26% of overall study population) or a 90-day medication refill cycle (~74% of overall study population).

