9.5 Data Analyses

The study team will use Humana claims data for outcome measurement, which contains information on prescription claims from pharmacies, as well as patient information. Regular linear regression will be used to compare outcomes between each intervention arm versus usual care adjusting for the stratified randomized design, age, gender, and race. These adjustments are necessary as the baseline differences in adherence in each of these groups could influence their responses to our intervention.

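### The 9.5 primary regression leaves out July PDC and supply status at Day 0, two baseline predictors obtainable from claims already held; the cost is precision, not bias

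*Combined protocol and SAP*

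**What the plan says.** **Entry.** Section 4.1 sets a PDC band of 60% to 85% and asks for "Having at least two unique fills of any class of hypertension medication within the calendar year". Section 6.2.1 states: "Eligibility decisions will be decided based on age and adherence level in July 2023". Nothing requires a recent fill or supply in hand when the first letter goes out.

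**Outcome and model.** The synopsis states: "The primary outcome will be the average end-of-year PDC in each arm". Section 9.5 fits a linear regression "adjusting for the stratified randomized design, age, gender, and race", and section 9.4.1 names the same set. Section 6.2.2 records July adherence as a baseline assessment, but it does not enter the model. Sections 9.2 and 9.4.2 provide for adjustment for whatever turns out imbalanced, in secondary analyses only.

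**Refill cycle.** Section 9.2.1 randomises "stratified by whether participants are on a 30-day" or a 90-day cycle, about 26% and 74%. Sections 9.1 and 9.4.1 also stratify the primary outcome by cycle.

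**Aim 2.** The synopsis will "evaluate the impact of the interventions as a function of baseline levels of adherence, demographic characteristics, and clinical comorbidities". The title of Aim 2 speaks more broadly of claims characteristics, and section 3 lists hypertension fills among the variables. No variable for supply on hand, run-out or stopping is defined anywhere.

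**The concern.** If end-of-year PDC covers the calendar year, much of it is already settled at Day 0, and most of the rest depends on whether the member keeps refilling. July PDC carries the first part. Supply status carries information on the second, because a member who ran out weeks ago is more likely to stay uncovered than one holding tablets. Section 9.5 justifies its covariates by baseline differences in adherence between groups, yet it uses age, gender and race and leaves out the adherence measurement itself.

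At stake is precision in six comparisons aimed at a difference of about 1 point. A lesser matter is Aim 2: within one level of baseline adherence, its listed modifiers do not distinguish a member who refills late from one who has run out.

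**Working it through.** **Assumptions.** The documents do not give the PDC window, the exact Day 0, the SD of PDC or the share out of supply. I take Day 0 as 15 July (day 196) and count PDC from 1 January unless stated otherwise.

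**1. The plan's own figure.** Section 9.2 gives 8,571 per arm for 80% power at a difference of about 1%. No SD is stated, so this cannot be reproduced directly. Read as a difference in means, two-sided at 0.05/6 (the first Holm step for six comparisons):

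n = 2(z₁ + z₂)² SD²/δ² = 2 × (2.638 + 0.842)² × SD²/1² = 8,571 gives SD ≈ 18.8 points.

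I use this SD only to translate variance into power. (Section 3 gives 7,143 per arm; that needs reconciling but does not affect this point.)

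**2. Weight of July PDC.** End-of-year PDC = (196 × July PDC + later covered days)/365. The weight on July PDC is 196/365 = 53.7%. The 25-point entry band alone therefore spreads end-of-year PDC by 25 × 0.537 = 13.4 points.

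**3. July PDC does not fix supply status in the 30-day stratum.** Two members start on 1 January and each has 150 covered days by 15 July, so both have 150/196 = 76.5%.

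| | Gap of 46 days | Later course (bounding case) | End-of-year PDC |
|---|---|---|---|
| Member A | in spring; covered on 15 July | every refill on time | (150 + 169)/365 = 87.4% |
| Member B | the last 46 days; out of supply | no further fill | 150/365 = 41.1% |

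These are limits, not forecasts.

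**4. The 90-day stratum differs.** Two used-up, non-overlapping 90-day fills give 180/196 = 91.8%, above the band. The figure drops below 85% only on day 212, 31 July (180/212 = 84.9%). So a 90-day member eligible in mid-July normally still holds supply, unless two classes overlapped, one fill was shorter, or Day 0 fell later. With two such fills and a first fill on 1 January, days on hand = 180 − 196 × PDC: 62 at 60%, 38 at 72.5%, 13 at 85%. In that case July PDC already determines days on hand. If PDC is counted from a later first fill, it does not: with 150 days observed and PDC 72.5%, days on hand = 180 − 150 × 0.725 = 71, against 38 above.

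**5. Size by formula.** Suppose run-out occurs only in the 30-day stratum, in a share p of it, with a gap of d points in end-of-year PDC. The variance share explained beyond refill cycle by a covered/run-out indicator alone is 0.26 × p(1 − p)d²/SD². With p = 30–35% (from the simulations below) and SD 18.8:

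- d = 10: 0.26 × 0.21 × 100/353 = 1.5%, to 0.26 × 0.2275 × 100/353 = 1.7%
- d = 20: four times as much, 6.2% to 6.7%

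**6. Size by simulation.** Twelve runs of refill histories: PDC from first fill, Day 0 at day 181 or 211, a 2% or 6% chance per 30 days of a long gap, and 0%, 30% or 60% filling two classes together. Reduction in residual variance relative to refill cycle alone, or to the model named:

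| Added | Reduction |
|---|---|
| July PDC, beyond cycle | 10–24% |
| Covered/run-out, beyond cycle and July PDC | 3–17% |
| Same, no overlapping classes | 3–7% |
| Same, plus days since run-out, all runs | 4–18% |

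Other assumed refill patterns gave 5–18%, 5–13% and 2–10% beyond cycle and July PDC. In the pattern giving 5–13%, the gain was 4–22% within the 30-day stratum and 4–5% within the 90-day stratum. In the twelve runs 90-day members were 51–64% of those eligible, not 74%, so the run-out part is probably somewhat overstated.

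**7. What 2–18% is worth.** Sample-size equivalent: 1/0.98 = 1.02 to 1/0.82 = 1.22, or 2–22% more participants. If 18.8 is the residual SD before supply status is added, power = Φ(3.480/√(1 − r) − 2.638), which is 81.0% at r = 2% and 88.6% at r = 18%, against 80.0%.

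**The case against.** The strongest reply is that the mixing is confined. For about 74% of participants the two-fill rule and the 85% ceiling together almost rule out run-out in mid-July, and the plan already stratifies and adjusts by the cycle that separates the two situations. In the simplest 90-day case, days on hand is a function of July PDC. The size rests on invented refill behaviour, and the worked pair is extreme. All of this stands, and it is why the range starts near 2%. It does not remove the point, because the 9.5 model contains no July PDC either, and in the 30-day stratum July PDC does not determine supply.

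A reader might infer three stronger things:

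- **That Aim 2 cannot tell which members respond.** It can do so by baseline adherence, demographics and comorbidities, and its title leaves room for other claims variables. The gap is only that late refillers and run-outs are not separated by the listed modifiers.
- **That many 90-day members are covered through both letters and see their score rise without acting.** On a 196-day count with two fills, 53 days on hand requires PDC of at most (180 − 53)/196 = 64.8%. On a count from first fill the share could be much larger. The documents do not fix the window, so no share is established.
- **That refill cycle is ignored.** It is the stratification factor and is in the primary analysis; it is missing only from the named Aim 2 modifiers.

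**Conclusion.** The point holds as one of efficiency. Two pre-randomisation predictors of the primary outcome are left in residual error although the claims that produce PDC supply both. July PDC is usually the larger omission (10–24% of residual variance beyond cycle in the simulations). Supply status adds roughly 2–18% beyond cycle and July PDC. These figures depend on assumed refill gaps, stopping rates, overlap between classes and PDC window; the direction does not, but the documents cannot settle the size, and the lower half is more plausible if 90-day members rarely run out. It would be wrong to infer biased arm contrasts: supply status is fixed before randomisation and balanced in expectation across the seven arms. The Aim 2 addition alone would be a matter of preference.

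**What to change.** In section 9.5, with 9.4.1 aligned, prespecify these baseline covariates for all seven arms, alongside those already listed:

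1. July PDC.
2. Days of supply on hand at Day 0 (zero if none).
3. For the 30-day stratum, days since supply ran out (zero if covered).

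Give each a separate slope by refill cycle where it applies to both. Derive them from fill dates and days' supply on claims dated before Day 0, using the coverage rule that defines PDC, including its handling of more than one class. State the PDC window and the date of Day 0. Tabulating supply status by cycle on pooled baseline data, before outcomes are examined, would replace the assumptions above with facts.

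Optionally, name as exploratory Aim 2 modifiers refill cycle and, within the 30-day stratum, covered versus run out at Day 0. A single three-level supply modifier across both strata is less useful, because it would largely repeat refill cycle.

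Cost: SAP wording, a few derived variables, a few degrees of freedom among about 60,000 participants, and one or two more exploratory interaction tests. Eligibility, letters and sample size are unchanged.

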1 STUDY OBJECTIVES

1.1 Primary Objective

Hypothesis: Messages using dynamic social norms, messenger effects, and processing fluency in combination will more effectively increase average end-of-year adherence level compared to usual care.

1.2 Secondary Objectives

Secondary objective: identify baseline clinical and demographic characteristics to predict the efficacy of each message.

2 BACKGROUND AND RATIONALE

2.1 Background on Condition, Disease, or Other Primary Study Focus

Hypertension substantially increases the risk of myocardial infarction and stroke,¹ but medications that can effectively control hypertension (are not always taken as prescribed: adherence rates for hypertension medications range from about 40% to 74% for most Americans.²⁻⁴ Non-adherence is therefore a potent contributor to preventable disability and death among middle-aged and older adults.⁵ There also exist disparities by race and ethnicity among Medicare Part D beneficiaries, Black and Hispanic patients are 38% and 45% more likely, respectively, to be nonadherent compared to white patients.⁶

2.2 Study Rationale

Interventions to improve medication adherence have had modest success;^{7,8} even the most effective interventions combining behavioral, educational, and logistical interventions for providers, health systems, and patients have limited effects.⁹⁻¹¹ Leveraging behavioral principles of social norms, messenger effects, and processing fluency may improve their impact.

Social norms describe perceptions about the behavior of others, which can influence one's own behavior. Making information about others' behavior more salient can encourage those behaviors when base rates are high. When they are low, dynamic norms, or information about how others' behavior is *changing*, may be more impactful.¹² Dynamic norms have shown impact in a range of healthy behaviors.¹³

The effectiveness of a message also often depends on who is communicating it. Messenger impact can differ depending on factors such as how trusted they are, or how much they have in common with the people they are communicating with. Messenger effects have been successfully leveraged in HIV prevention and management¹⁴ and diabetes screening.¹⁵ Leveraging pharmacists in hypertension medication adherence interventions has shown promise, mainly in direct phone calls from pharmacists.^{16,17} Having medication-related messaging come from an insurance company's pharmacist rather than the insurance company itself may increase its impact, especially with pharmacists who are taking the same medications, and with lower cost through written communication rather than a phone call.

Processing fluency is the subjective ease with which information is understood, which can influence its actionability. Increasing processing fluency has been impactful for exercise¹⁸ and other health behaviors,¹⁹ including treatment adherence for juvenile idiopathic arthritis²⁰ and cancer screening.²¹ Studies providing patients with summary information for statin medication adherence have demonstrated null²² or limited²³ results, but incorporating measures to ease processing fluency through tactics such as visual metaphors that emphasize goal progress and attainability may increase their impact, especially as low health literacy is a key barrier to medication adherence.²⁴

Messages may have varied effectiveness based on patients' level of adherence and/or demographic factors, which are also associated with differences in adherence.^{4,6} Tailoring a message based upon these factors could optimize future intervention effectiveness.

Thus, the study team proposes a randomized trial to test the effects of mailed communication leveraging social norms, messenger effects, and processing fluency on hypertension medication adherence for patients who are not fully adherent, followed by analyses identifying intervention responsiveness by patient characteristics.

3 STUDY DESIGN

Type/design of trial: randomized controlled trial

Primary objective (hypothesis): Messages using dynamic social norms, messenger effects, and processing fluency in combination will more effectively increase average end-of-year adherence level compared to usual care (no messages).

Secondary objective: To identify baseline clinical and demographic characteristics to predict the efficacy of each message.

Study population: Individuals 65 to 79 years of age taking any class of medication for hypertension, with adherence level between 60% and 85%.

Study arms (7,143 individuals each):

1. A scorecard from Humana reporting patients' medication adherence using a "refill score"
2. The Arm 1 scorecard plus dynamic social norms messaging (noting the proportion of Humana members improving their medication refill scores)
3. The Arm 1 scorecard, coming from the trusted messenger of a Humana-identified pharmacist taking the same medication.
4. A modified scorecard increasing processing fluency through a visual metaphor of "closing the ring"
5. The Arm 4 scorecard plus dynamic social norms messaging
6. The Arm 4 scorecard, coming from the trusted messenger of a Humana-identified pharmacist taking the same medication.
7. No mailed message (usual care)

Study location: Humana

Duration of enrollment period: Individuals will be enrolled at a single time point at study launch

Duration of follow-up period: Approximately 6 months

Description of intervention and administration: Study participants will be randomized into receiving one of 6 mailed messages (arms 1-6 above) informing them of their medication refill score, or no message. Two messages will be sent during the intervention: The first message will contain the baseline refill score. The second message will note any changes in the refill score.

Description of descriptive and outcome variables from the medical, insurance, and pharmaceutical records:

Medical variables: None

Insurance / enrollment variables:

- Patient enrollment in a Medicare Advantage Prescription Drug plan insured by Humana in plan year 2023
- Patient age in plan year 2023
- Patient Gender
- Patient Race

Pharmaceutical variables:

- Current adherence on hypertension medications (PDC) as of July 2023
- Unique prescription fills for hypertension medication use
- Unique prescription fills for other medications
- End-of-year adherence on hypertension medications (PDC) in 2023 (following intervention)

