9.2 Sample Size and Randomization

The study team estimates a sample size of 59,997 (8,571 per arm) will provide 80% power to observe a ~1% difference in end-of-year adherence level compared to the usual care arm, conservatively assuming a usual care arm rate of 70% and a Holm-Bonferroni corrected alpha of 0.05 to adjust the familywise error rates for multiple hypotheses testing. This difference is significant as the focus of CMS Star ratings measure interventions and are comparable to improvements seen in other similar large-scale behavioral communication studies. In secondary analyses, the study team will compare arms against each other and adjust for any imbalanced baseline characteristics.

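### If the primary outcome is cumulative 2023 PDC, about half of it is fixed before the first letter, and the regression leaves out the July PDC that would absorb that part

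*Combined protocol and SAP*

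**What the plan says.** The Design and Outcomes summary states: "The primary outcome will be the average end-of-year PDC in each arm". The variable list in section 3 gives two PDC measurements: "Current adherence on hypertension medications (PDC) as of July 2023" and "End-of-year adherence on hypertension medications (PDC) in 2023 (following intervention"). Section 6.2.1 adds: "Eligibility decisions will be decided based on age and adherence level in July 2023". Under Interventions and Duration, follow-up is given as: "Participants will participate in this study for approximately 6 months (through December 2023"). The schedule in section 6.1 places the letters at "Treatment 1 (Day 1") and "Treatment 2 (Day 53"), with no calendar date for either.

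Section 9.2 claims "80% power to observe a ~1% difference in end-of-year adherence level compared to the usual care arm". Sections 9.4.1 and 9.5 adjust the linear regression for refill-cycle stratum, age, gender and race. July PDC is a baseline assessment (section 6.2.2) and an eligibility criterion (section 4.1), but it is not in the model.

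**The concern.** No section gives the first and last day over which PDC is computed. Three features favour one running calendar-year measure:

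- Section 4.1 counts qualifying fills within the calendar year.
- Section 9.2 justifies the target effect by CMS Star ratings.
- Sections 3 and 5.1 have the second letter report how the refill score has changed.

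On that reading, the days before Day 1 enter the outcome but no letter can alter them. This has two consequences. First, an effect on post-mailing adherence appears in the primary outcome at about half its size, which a reader of section 9.2 is not told. Second, the settled days carry each member's baseline adherence into the outcome as noise. The one variable that would remove that noise is already held and is left out, although section 9.5 justifies its other adjustments by baseline differences in adherence. Precision is given away in all six comparisons with usual care.

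**Working it through.** **The plan's own figure.** The 80% power in section 9.2 cannot be reproduced for a mean, because no SD is given. Solving 1 = (z for alpha + z for power) × SD × √(2/8,571) for a 1-point difference gives:

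- SD = 23.4 at two-sided 0.05 (sum of z-values 2.80).
- SD = 18.8 at two-sided 0.05/6, the first Holm step (sum 3.48).

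Neither SD is in the documents. Reading the 70% usual-care figure as a proportion (70% v 71%) gives power of 30% and 11% at those two levels. That is a separate question. What matters here is that the ~1% is on the end-of-year scale.

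**Share already fixed.** Let T be the days in the PDC window and p the days from mailing to 31 December. The fixed share is (T − p)/T, and the post-mailing change needed for one end-of-year point is T/p. The dates are assumptions: a July mailing, because eligibility is set in July and follow-up is about 6 months, and a window starting on 1 January or at a later first fill.

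| Window start | Mailing | T | p | Fixed | Points needed |
|---|---|---|---|---|---|
| 1 Jan | 1 Jul | 365 | 184 | 49.6% | 1.98 |
| 1 Jan | 15 Jul | 365 | 170 | 53.4% | 2.15 |
| 1 Jan | 31 Jul | 365 | 154 | 57.8% | 2.37 |
| 31 Jan | 1 Jul | 335 | 184 | 45.1% | 1.82 |
| 1 Mar | 1 Jul | 306 | 184 | 39.9% | 1.66 |
| 1 Mar | 31 Jul | 306 | 154 | 49.7% | 1.99 |

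Supply already in hand at mailing, especially on 90-day fills (about 74% of members), would raise the needed change further. The documents do not allow that to be quantified.

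**Gain from adding July PDC.** Let B be July PDC and P post-mailing PDC, with P = a + bB + e. The outcome is Y = [(T − p)B + pP]/T. With r = (T − p)/p:

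- Variance of Y without B in the model: (p/T)² × [(r + b)² Var(B) + SD(e)²].
- Variance with B in the model: (p/T)² × SD(e)².
- Ratio of z-statistics, adjusted to unadjusted: √[1 + (r + b)² Var(B)/SD(e)²].

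Assumed inputs: B uniform on 60-85%, so Var(B) = 25²/12 = 52.08; SD(e) 20-25 points; b from 0 to 1; window from 1 January.

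- Smallest gain (1 July, b = 0, SD 25): r = 181/184 = 0.984, and √(1 + 0.968 × 52.08/625) = √1.081 = 1.04.
- Largest gain (31 July, b = 1, SD 20): r = 211/154 = 1.370, and √(1 + 2.370² × 52.08/400) = √1.731 = 1.32.

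The z-statistic therefore rises by about 4-32%, equivalent to 8-73% more participants (the squared ratios). If every window began on 1 March, r at a 1 July mailing would be 122/184 = 0.663 and the smallest gain would be about 2% (√1.037). If PDC were counted only after mailing, r = 0 and the gain would run from nothing (b = 0) to about 6% (b = 1, SD 20: √1.130).

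**The case against.** The cumulative window is an inference. The words about following the intervention in section 3 can be read as a window that opens at mailing, in which case there is no dilution. That stands, and it is why the size of the point is conditional. Adding July PDC is useful or harmless on either reading.

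A reader might infer four stronger things that the documents do not support.

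- **That more than half of the outcome is fixed.** A 1 July mailing with a 1 January start fixes 49.6%, and a later first fill fixes less. About half is what six months of follow-up supports.
- **That a point of annual PDC needs up to 2.6 points after mailing.** That requires mailing around 15 August (365/139 = 2.63), about 4.6 months before year end, which fits poorly with July eligibility and about six months of follow-up.
- **That the section 9.2 calculation is wrong, or that the trial would miss a letter meeting the stated 1%.** The ~1% is defined on end-of-year adherence. A letter adding one point only to post-mailing days has not met it. Dilution bears on how plausible and interpretable that target is, not on its arithmetic.
- **That post-mailing PDC must become the primary outcome.** Year-end PDC is a coherent target for an insurer working to Star ratings. Once July PDC is in the model, the two windows give equal power, because the adjusted annual outcome is the post-mailing outcome rescaled by p/T. The recoverable efficiency loss comes from the missing covariate, not from the window.

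The precision gain also depends on how strongly post-mailing PDC follows July PDC. Regression to the mean is plausible in a group selected on 60-85%, so a slope near 1 should not be presumed. The range above therefore runs from 0 to 1.

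**Conclusion.** The point holds in conditional form. If PDC is cumulative over 2023, roughly 40-58% of the primary outcome is settled at randomization, and one end-of-year point corresponds to about 2 points of post-mailing change (1.7-2.4). This rests on a July mailing and a first fill between 1 January and 1 March. Omitting July PDC forgoes about 4-32% in the z-statistic under the stated assumptions, with the low end nearer 2% if windows start later. The documents give neither an SD nor a correlation, so these figures are illustrative. Within the assumed ranges the adjustment never reduces the z-statistic.

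**What to change.** Keep end-of-year 2023 PDC as the primary outcome and make these changes before outcome data are examined:

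1. In sections 9.4.1 and 9.5, add July 2023 PDC as a covariate in the primary regression.
2. In section 3, state the first and last day of the PDC window and the calendar date of Day 1.
3. In section 9.2, say that ~1 point of end-of-year PDC corresponds to roughly 2 points of post-mailing PDC (range 1.7-2.4), updated once the dates are fixed.
4. In section 9.4.2, add post-mailing PDC (Day 1 to 31 December 2023, same index date for usual care) as a secondary outcome.

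The covariate is already collected and costs one degree of freedom. The secondary outcome needs one more calculation from the same claims. The only burdens are a second PDC window to report and a detectable effect that looks less favourable once expressed on post-mailing days.
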